9.2.5 Post-Injection phone contact

The patient must be contacted by phone after 24-hour (\pm 4 hours) after each contrast injection. The two MRI contrast agents will be separated by at least 24 hours, but not more than 15 days.

26 MAR 2019 Version no. 2.0 Page: 28 of 60

Any TEAEs or TESAEs and/or concomitant medications reported during this period will be recorded in the eCRF.

The end of Study Period 2 is after the 24 hour post injection AE follow-up phone call.

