5.1 Design overview

This study is a Phase 4, multicenter, controlled, cross-over study with corresponding blinded image evaluations in male and female patients at least 18 years of age, who are referred for a contrast-enhanced MRI of the CNS based on a known or highly suspected lesion of the CNS.

Patients will undergo an unenhanced and contrast-enhanced MRI of the CNS using gadoterate at the standard dose of 0.1 mmol/kg BW. If the investigator does not identify an enhancing lesion of the CNS, then this patient will be considered a screening failure. If an enhancing lesion is identified, then the patient will undergo a second unenhanced and contrast-enhanced MRI of the CNS using gadobutrol at a dose of 0.075 mmol/kg BW.

Safety will be assessed from the first administration of gadoterate through 24 hours after the second administration of gadobutrol. Adverse events will be collected from the signing of informed consent through the end of the follow-up period. Serious adverse events (SAEs) will be followed through resolution. Patients who receive only the first MRI scan (considered screening failures) will be followed for SAEs only.

Gadobutrol will be administered at the dose of 0.075 mmol/kg body weight by single IV injection at a rate of 2 mL/sec, followed by 20-mL 0.9% saline flush at the same rate. Gadoterate will be administered at the approved standard dose of 0.1 mmol/kg body weight by single IV injection at 2 mL/sec, followed by 20-mL 0.9% saline flush at the same rate. The 2 injections will be separated by at least 24 hours, but not more than 15 days.

During the course of the study, 2 MRIs will be obtained from each patient as follows: before the administration of each of the contrast agent (unenhanced MRI) consisting of steady-state sequences (T1w, T2w, and FLAIR), following the gadoterate injection (gadoterate-enhanced MRI) consisting of steady-state sequences T1; and following the gadobutrol injection (gadobutrol-enhanced MRI) consisting of steady-state sequences (T1w).

The unenhanced MR image set, combined unenhanced and gadobutrol-enhanced MR image sets, and the unenhanced and combined unenhanced and gadoterate-enhanced MR image sets will be evaluated by 3 independent blinded readers. The blinded readers will also evaluate the

26 MAR 2019 Version no. 2.0 Page: 15 of 60

gadobutrol-enhanced T1w images compared to the gadoterate-enhanced T1w images in a paired read for image quality.

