9.1 Tabular schedule of evaluations

Table 9-1 displays the schedule of evaluations and procedures for the study.

26 MAR 2019 Version no. 2.0 Page: 24 of 60

Table 9-1: Schedule of Study Events

		Stu	udy Period 1 ^a			Stud	dy Period 2 ^a		
Evaluation/Procedure	Baseline ^b	MR	I	Post Injection Phone Contact ^c	Baseline ^C	MR	I	Post Injection Phone Contact ^c	Final Diagnosis up to 30 days Phone call
Time Point	Up to 72 hours prior to the 1st MRI	Unenhanced	Enhanced	24h±4h	Within 24 h of the 2 nd MRI	Unenhanced	Enhanced	24h (±4 h)	Thorne can
Sign informed consent	Х								
Demographic data	X								
Medical/surgical history	X								
Baseline findings	X								
Referral diagnosis	X								
Previous/concomitant medications ^d	X			X	×			Х	
Weight ^e	χi				χi				
Urine pregnancy test ^f	χi								
Creatinine value ^g	X								
Gadoterate administration			Х						
Gadobutrol administration							Х		
Adverse event monitoring	X	Х	Х	Х	Х	Х	Х	Х	
Final clinical diagnosis up to 30 day post first MRI ^h									Х

Clinical Study Protocol

No. BAY No. 86-4875/ IMPACT no. 19773

26 MAR 2019 Version no. 2.0 Page: 25 of 60

Abbreviations: h = hour(s); immed = immediately; inj = injection; min = minutes

Notes:

- ^a A period of 24 h up to 15 days is required between the contrast agent injections;
- b Baseline for study period 1 is from after signing informed consent up to 72 hours for gadoterate administration;
- ^c Baseline for study period 2 is within the 24 h prior to administration of gadobutrol. At least 2 h is required between the 24-h follow-up evaluations from study period 1 and the baseline evaluations for study period 2. The patient will be contacted by phone after 24-hour (± 4 hours) after each contrast agent injection. The two MRI contrast agents will be separated by at least 24 hours, but not more than 15 days. Any TEAEs or TESAEs and/or concomitant medications reported during this period will be recorded in the eCRF.
- d All concomitant medication will be collected
- ^e Weight will be obtained at baseline and reconfirmed prior to the second MRI
- f Urine pregnancy test (if applicable) to be done at the site, according to the standard of the institution, and the results must be available prior to the gadoterate MRI.
- g Serum creatinine (eGFR value calculated using either MDRD or the CKD-EPI Creatinine Equation, 2009) derived up to 4 weeks prior to the first study MRI value and date obtained and method used needs to be recorded at Screening.

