9.2 Study periods

9.2.1 Baseline study period 1

Baseline is the up to 72 hour period from signing informed consent to administration of gadoterate (including saline flush).

Prior to administration of gadoterate the following will be performed: placement of IV injection line, urine pregnancy test (in women of child bearing potential the date and time of the pregnancy test sample and the result of the pregnancy test will be recorded in the eCRF). Results of the pregnancy test must be negative prior to the administration of any contrast agent.

The IV injection line will consist of a large bore indwelling catheter (at least 18 gauge) preferably placed in an antecubital vein. The location of the IV injection line must be documented in the eCRF.

9.2.2 Study period 1

The administration of gadoterate is study period 1 and the administration of the gadobutrol is study period 2.

The following procedures will be performed during study period 1:

- 1. An unenhanced MRI of the brain will be performed according to the standards of the institution.
- 2. The appropriate volume corresponding to 0.1 mmol/kg of gadoterate will be administered IV as a bolus injection at the rate of 2 mL/sec using a power injector via a peripheral vein (the antecubital vein is preferred) followed by a 20-mL 0.9% saline flush using a power injector at the same flow rate. The dose and volume of the contrast agent will be recorded.
- 3. AE monitoring will begin at baseline. All TEAEs will be monitored for 24 hours after the administration of each contrast agent. However, if no enhancing lesion is identified in the first imaging study, the patient will not be included in the safety database and only SAEs for that patient would be reported.
- 4. Conventional steady-state contrast-enhanced imaging with a T1w sequence according to the parameters listed in Section 10.2.1.2 will start 4 to 10 minutes following the injection of the contrast agent.
- 5. The patient will be asked about his/her physical condition. Any clinically significant changes in the patient's physical condition from the baseline values are to be recorded in the eCRF, and the TEAE section is to be completed accordingly.

26 MAR 2019 Version no. 2.0 Page: 27 of 60

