10.4.1.3 Assessments and documentation of adverse events

The investigator must record on the respective CRF pages all adverse events occurring in the period between the signing of the informed consent and the end of the follow-up phase; all SAEs/TESAEs must be followed to resolution. After the end of the follow-up phase there is no requirement to actively collect TEAEs including deaths. The type of information that should be assessed and recorded by the investigator for each TEAE is listed in Section 10.4.1.2.

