6.4.2.1 Overview of AEs

The number and percentage of subjects experiencing AEs will be summarized. Overall summary tables will be provided for all AEs, TEAEs and pretreatment AEs with following categories:

- Any such AEs
- Drug-related AEs
- AEs related to procedures required by the protocol
- AEs by intensity (mild, moderate, severe)
- Drug-related AEs by intensity
- Serious AEs (SAEs)
- Drug-related SAEs
- SAEs related to procedures required by the protocol
- AEs leading to discontinuation of study drug
- SAEs leading to discontinuation of study drug
- AEs leading to death.

The overall summary table will also be presented on AEs of subjects only receiving gadoterate but not included in the SAF.

The number and percentage of subjects with TEAEs will be summarized for the following:

- TEAEs and treatment-emergent SAEs (TESAEs) by SOC and PT
- Drug-related TEAEs and TESAEs by SOC and PT
- Nonserious TEAE by SOC and PT
- TEAEs and TESAEs resulting in discontinuation of study drug by SOC and PT
- TEAEs and TESAEs by maximum intensity, SOC, and PT
- Drug-related TEAEs and TESAEs by maximum intensity, SOC, and PT
- TEAEs and TESAEs by worst outcome, SOC, and PT
- Drug-related TEAEs and TESAEs by worst outcome, SOC, and PT

Common TEAEs, TESAEs, drug-related TEAEs, and drug-related TESAEs with frequency $\geq 1\%$ by SOC and PT.

Tables will be sorted alphabetically by SOC and PT.

Subject listings of all AEs as well as subset listings of AEs leading to death and AEs resulting in discontinuation of study drug will be created.

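### The closing AE call may fall at 20 h, so the stated 24 h of TEAE monitoring is not guaranteed after gadobutrol, and only gadoterate has later scheduled AE enquiries

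*Protocol*

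**What the plan says.** **Stated window.** Protocol 5.1: "Safety will be assessed from the first administration of gadoterate through 24 hours after the second administration of gadobutrol". Protocol 9.2.2, item 3: "All TEAEs will be monitored for 24 hours after the administration of each contrast agent". Sections 8.1 and 10.1.3 also run the recording of concomitant medication to 24 h after the second agent.

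**Timing of the contact.** Notes to Table 9-1: "The patient will be contacted by phone after 24-hour (± 4 hours) after each contrast agent injection". The tolerance is the same for both agents.

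**After gadobutrol.** Protocol 9.2.5: "The end of Study Period 2 is after the 24 hour post injection AE follow-up phone call". In Table 9-1 the row "Adverse event monitoring" is blank under the final-diagnosis phone call. Protocol 10.4.1.3: "After the end of the follow-up phase there is no requirement to actively collect TEAEs including deaths". The same section requires follow-up to resolution only for serious events.

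**After gadoterate.** Table 9-1 marks AE monitoring again at Baseline 2 and at the second unenhanced MRI. Baseline 2 is a separate, later contact: "At least 2 h is required between the 24-h follow-up evaluations from study period 1 and the baseline evaluations for study period 2". Protocol 7.2 states that the order of the agents is not randomized; gadoterate always comes first.

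**Analysis.** SAP 6 ends each treatment-emergent (TE) period at 24 ± 4 hours after injection and classes the interval between the two TE periods as post-treatment. SAP 6.4.2 attributes an AE to an agent by its onset or worsening within the TE period. Protocol 10.4.1.1 defines a TEAE without any upper time limit. SAP 6.4.2.1 plans tables of "TEAEs and TESAEs by worst outcome, SOC, and PT".

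**The concern.** A site can follow the schedule exactly and still not observe the whole window that the protocol states. After gadobutrol no later scheduled enquiry closes the gap. After gadoterate one exists for every patient who goes on to the second period.

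Because the order is fixed, the extra enquiries always fall to the comparator and cannot balance out across sequences. Two by-agent summaries could be touched. One is the TEAE count, through events that start late or are remembered late. The other is the worst-outcome table, because a non-serious event still ongoing at the gadobutrol call has no scheduled update. Describing the safety profile of both agents is a stated secondary objective, so differences that come from the contact schedule should be kept out of it.

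**Working it through.** No sample size, power or alpha figure is involved. The check sets the documents' visit times against the stated 24 h.

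**1. Guaranteed coverage after gadobutrol.** Call window = 24 ± 4 = 20 h to 28 h. With the earliest compliant call, the gap is 24 − 20 = 4 h, and 4/24 = 16.7% of the stated window. With a call at 24 h to 28 h the gap is zero. So the stated 24 h can be met, but only 20 h is assured.

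**2. Scheduled AE contacts, counted from Table 9-1.**

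| After | AE monitoring marked at | Number |
|---|---|---|
| Gadoterate, before the next injection | enhanced MRI 1, call 1, Baseline 2, unenhanced MRI 2 | 4 |
| Gadobutrol | enhanced MRI 2, call 2 | 2 |

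**3. When the extra gadoterate contact falls.** Baseline 2 is at least 2 h after the first call: at the earliest 20 + 2 = 22 h, or 28 + 2 = 30 h after a late call. The second injection comes between 24 h and 15 days (15 × 24 = 360 h). A patient who continues therefore has scheduled AE contact up to an injection that cannot come before 24 h.

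**4. Outcome of non-serious AEs.** The last scheduled opportunity to record resolution of a gadobutrol event is the call, at 20 h to 28 h. A gadoterate event can be updated up to the second injection, as late as 360 h.

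**5. How many onsets could fall in the gap.** Protocol 10.4.1.4 says only that the majority of TEAEs occur within 30 minutes. Assume that a share m of 24 h TEAEs starts in the first 0.5 h and the rest is spread evenly over the remaining 23.5 h.

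- Every call at 20 h: share in the gap = (1 − m) × 4/23.5.
- Calls spread evenly over 20 h to 28 h: half fall before 24 h with a mean gap of 2 h, so the overall mean gap is 0.5 × 2 = 1 h and the share is (1 − m) × 1/23.5.

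| m (assumed) | Every call at 20 h | Calls spread over 20–28 h |
|---|---|---|
| 50% | 8.5% | 2.1% |
| 70% | 5.1% | 1.3% |
| 90% | 1.7% | 0.4% |

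The documents give neither the onset distribution nor the distribution of call times, so this is a range and not an estimate.

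**6. What the SAP's TE period does to the count.** The text allows two readings of 24 ± 4 hours. If the TE period ends at the actual call, a gadoterate event that starts between the call and Baseline 2 is post-treatment, and Baseline 2 can add only events that began earlier and were remembered late. If it runs to 28 h for everyone, gadoterate onsets between an early call and 28 h can be picked up at Baseline 2 and counted, while gadobutrol onsets after an early call have no scheduled enquiry. The protocol's open-ended TEAE definition would widen the difference further.

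**The case against.** The strongest reply has four parts.

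- **The call is not the only AE contact after gadobutrol.** Protocol 9.2.4, item 4, has the patient asked about physical condition after the injection, Table 9-1 marks AE monitoring at the enhanced MRI, and 10.4.1.4 sets at least 30 minutes of continuous supervision. This stands. The call is the last scheduled contact, and the only one after the imaging visit.
- **Recording does not formally stop at the call.** Protocol 9.2.5 ends Study Period 2, and SAP 6 runs the post-treatment period to the last study record, so an event that is volunteered later can be entered. This also stands. What is missing is a scheduled question.
- **The SAP limits any bias in counts.** TE periods are worded identically for both agents and attribution is by onset. This stands in large part, but the end of the TE period is not fixed, and onset-based attribution does not remove late recall or later outcome updates.
- **Little is at stake.** Most TEAEs are expected within 30 minutes, and the safety comparison is descriptive with no test. This stands and sets the weight of the point.

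A reader might infer more: that 24 h of monitoring is not delivered, that gadoterate loses nothing, or that the gadobutrol TEAE count is biased downwards. The documents do not support these. A call at or after 24 h delivers the window. A patient who drops out after the first MRI may have no Baseline 2, and for others it can come up to about 15 days later and depends on recall. The direction of any difference is a possibility, and nothing in the documents says how often calls fall before 24 h.

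**Conclusion.** The point holds in limited form. After gadobutrol the schedule guarantees 20 h of AE enquiry against a stated 24 h, so up to 4 h (17%) may have no later scheduled contact. In addition, the fixed order gives late-recalled events and outcome updates of non-serious AEs a scheduled route for gadoterate, in patients who continue, and none for gadobutrol.

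The effect on TEAE counts is probably small and its size is unknown. Under the assumptions above, 0.4% to 8.5% of onsets within 24 h would fall in the gap. The worst-outcome tables are more exposed, because the difference in follow-up there is 20–28 h against up to 360 h and onset-based attribution does not correct it. No efficacy conclusion is affected. This is an inconsistency that can be removed at low cost, and not evidence of a distorted safety result.

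**What to change.** Reconcile Protocol 5.1, 9.1 (Table 9-1 and notes), 9.2.2, 9.2.5 and 10.4.1.1 with SAP 6:

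1. **One end of the TE period.** State a single fixed end, identical for both agents, in place of 24 ± 4 hours, and use it in the protocol's TEAE definition as well. The protocol already names 24 h. As injections may be only 24 h apart, a later end could overlap with the gadobutrol period.
2. **A closing contact that covers it.** Either require the closing AE data-collection contact after gadobutrol to fall no earlier than the stated 24 h, or mark AE monitoring in the existing final-diagnosis phone-call column of Table 9-1, asking for events with onset in that window and for the outcome of ongoing AEs. The first option protects onset counts better: the final-diagnosis contact can come up to 30 − 1 = 29 days after gadobutrol, when recall is weaker. The second also supplies the missing outcome update.
3. **Reporting.** Give actual call times by agent. Add a version of the by-agent worst-outcome tables with outcome taken at the post-injection call for both agents, and keep later outcomes in the listings so that no information is lost.

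**Cost.** Changes to schedule and SAP wording, no new visit. The first option in item 2 narrows the gadobutrol calling window (24 h to 28 h if the upper limit stays) and makes it differ from the gadoterate window, which is one reason to report call times. The second adds a few eCRF entries. Items 1 and 3 can still be done in the analysis once data are collected, provided that the eCRF holds the call times and dated outcomes.

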9.2.6 Final clinical diagnosis

The final clinical diagnosis and whether this represents malignant disease will be determined by the investigator using all available clinical information available up to 30 days post-first MRI.

10. Procedures and variables

10.1 Population characteristics

Male and female patients of any ethnic group, who meet the inclusion criteria and none of the exclusion criteria, will be eligible for enrollment into the study.

10.1.1 Demographic

Demographic data (year of birth, age, sex, ethnic group), height, weight, baseline findings, and the suspected or known referral diagnosis according to Table 10-1 will be obtained at baseline.

Table 10-1: Referral Diagnosis of CNS Lesions

- Meningioma
- Anaplastic/malignant meningioma
- Glial tumor, low grade (I/II)
- Glial tumor, high grade (III/IV)
- Glial tumor, tumor grade cannot be determined
- Metastases
- Multiple sclerosis (acute and chronic)
- · Optic neuritis
- Meningeal disease (focal enhancement)
- Pituitary adenomas (macro and micro)
- Craniopharyngiomas
- Tumors of the choroidal plexus
- · Tumors of the pineal gland
- Meningeal carcinomatosis
- Oligodendrogliomas grade II
- Oligodendrogliomas grade III (anaplastic/malignant)

- Chordomas
- Primary lymphoma
- Dermoid/Epidermoid tumors
- Infectious disease (eg, brain abscess, cisticercosis, etc)
- Venous angiomas
- Meningeal spread of meningiomas (dural involvement)
- Cerebelopontine angle tumors
- Von Hippel Lindau syndrome
- Hypertensive leukoencephalopathy
- Subacute/chronic ischemia
- Encephalitis
- Others, specify
- Not assessable

26 MAR 2019 Version no. 2.0 Page: 29 of 60

10.1.2 Medical history

Medical history findings (i.e. previous diagnoses, diseases or surgeries) meeting all criteria listed below will be collected as available to the investigator:

- Start before signing of the informed consent
- Considered relevant for the patient's study eligibility.

Detailed instructions on the differentiation between (i) medical history and (ii) adverse events can be found in Section 10.4.1.1.

10.1.3 Prior and concomitant medications

Any medication received within 72 hours prior to the first contrast agent through 24 hours after the second contrast agent will be recorded in the eCRF, including the drug name (brand name is preferred), indication, total daily dose, route of administration, and start and stop dates. Any changes in concomitant medication will also be recorded.

No contrast agent is allowed to be administered within 24 hours prior to the study MRIs or during the study period.

10.2 Efficacy

10.2.1 MRI procedures

10.2.1.1 MRI equipment — AMENDED

The procedure will be performed using either a 1.5 or a 3.0 Tesla MRI scanner that can perform the required pulse sequences (see Section 10.2.1.2) with a dedicated head coil. The manufacturer, model, software version, and field strength of the MRI device will be recorded in the eCRF. The same scanner and required pulse sequences must be used for both the gadoterate and gadobutrol enhanced MRI's.

The same field strength (either 1.5 or 3.0) must be used for both scans. Mixed field strength scans are not permitted.

In addition, T1w enhanced sequences must be performed at or near the same post-dose timepoint (4-10 mins) for each study drug (gadoterate and gadobutrol).

10.2.1.2 Pulse sequences — AMENDED

The same parameter setting must be used for unenhanced T1w images and for contrast-enhanced T1w images in each patient.T1w spin echo/FSE acquisition should be performed in 2D mode. The required pulse sequences for gadobutrol and gadoterate are:

- Unenhanced (axial and sagittal image presentation for brain)
 - o T1w spin-echo/FSE images of the whole brain axial
 - o Fluid Attenuated Inversion Recovery (FLAIR) of the whole brain axial

26 MAR 2019 Version no. 2.0 Page: 30 of 60

- Optional: T2w spin-echo images of the whole brain sagittal or axial
- Contrast-enhanced (axial and coronal image presentation for brain)
 - o T1w spin echo/ FSE images of the whole brain
- General considerations
 - o The MR scanner should NOT be actively retuned after the unenhanced sequences

Deviations from the specified MRI procedure will be recorded in the eCRF.

10.2.1.2.1 Sequence parameters for brain imaging — AMENDED

The recommended sequence parameters for brain imaging is displayed below in Table 10-2.

T2 SE/FSE T1 **FLAIR** Plane Sagittal or Axial Axial or Coronal Axial IR Pulse Sequence Spin echo/FSE Spin echo/FSE Patient position Supine Supine Supine Coil Head Head Head Slice thick/spacing 3-5 skip 0-1.5 3-5 skip 0-1.5 3-5 skip 0-1.5 Frequency ≥256 ≥256 ≥256 Phase ≥256 ≥256 ≥128 Nex ≥2 ≥2 ≥1

Table 10-2: Orientation parallel to the planum sphenoidale (only for axial) — AMENDED

